 - c. *H2_c: Relative to historical matched controls drawn from previous years of the program, participants receiving sessions will demonstrate greater reductions in HIV sexual risk behavior.*
- 3) **Secondary Aim:** Estimate the effect of MoodGym on the uptake/adherence to ART and PrEP among HIV-positive and HIV-negative participants, respectively.
 - a. *H3_a: Increased attendance to sessions will be associated with lower comorbid depression scores which, in turn, will be associated with increased likelihood of ART medication uptake and/or adherence for HIV-*

positive participants as well as increased likelihood of PrEP uptake and/or adherence for HIV-negative participants.

INTRODUCTION

[figure not shown]
Background

Each year, 70% of new HIV infections in the United States occur with MSM,¹ and use is identified as a major driving force in the continued HIV/AIDS pandemic affecting MSM communities.² Though studies have consistently demonstrated associations between use and HIV transmission among MSM,^{3,4} recent research has further illustrated that depression is likely an under-recognized mechanism in the /HIV link, statistically both mediating and moderating the link between use and engagement in sexual risk behaviors.⁵ Further, depression is an obstacle to medication adherence for both HIV-positive and HIV-negative MSM; depression has been associated with reduced adherence to ART medication,^{6,7} and MSM in the iPrex study with the highest levels of depression also demonstrated the lowest levels of PrEP adherence,⁸ highlighting the important effects of depression on biobehavioral efforts to limit HIV transmission among MSM.

STUDY DESIGN

This study is a single-arm, non-randomized pilot study. Eligible participants are newly enrolled Getting Off service program participants who will be invited to participate in the study during their enrollment, and can enroll in the study at any time during their first two weeks of program participation (see Figure 1).

Figure 1: Study Design “Depression Intervention to Optimize Methamphetamine Treatment Outcomes among Gay and Bisexual Men”

Study activities will take place contemporaneously with participation in the service program (i.e., participants enroll during their first or second week of Getting Off, and

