complete the 5 sessions over the remaining 6-7 weeks). If participants complete all five MoodGym modules prior to the 8-week endpoint, they will be offered the chance to revisit prior module(s); assessments and incentives will continue as scheduled. Getting Off program evaluation data from study participants will be matched and compared with historical program evaluation data to assess the impact of the MoodGym intervention on the Getting Off program outcomes through an observed treatment effects analysis.

MoodGym

MoodGym is a seven module computer-optimized, evidenced-based intervention for adults with depression and/or anxiety symptoms. Though MoodGym modules can be taken by participants without assistance, evidence suggests results may be improved by applying in a more structured setting. In this pilot study, MoodGym will be delivered with support and guidance from a trained Study Counselor. Each week participants will be asked to attend one one-hour individual appointment with the Study Counselor to complete a MoodGym module, for up to seven weeks.

Phone Call After One Missed Session of MoodGym

The SC will monitor participant attendance and conduct a phone call to any participant who does not attend a scheduled session, to reschedule.

SELECTION AND ENROLLMENT OF PARTICIPANTS

Inclusion Criteria

- A participant enrolled in the Getting Off service program at Friends Community Center; and,
- Within his first or second week in the program

Exclusion Criteria

- Not a participant in his first or second week of the Getting Off service program at Friends Community Center

STUDY PROCEDURES

Recruitment and Enrollment

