Specific statistical analyses will be chosen based on the distributional properties of the variables being analyzed; sociodemographics or other variables found to significantly influence primary outcomes may be tested for inclusion as statistical controls and/or bases for contingency analyses. The outcome of primary analytical interest, i.e., engagement in HIV sexual risk behaviors, is most amenable to analyses employing the negative binomial or logistic link functions, for count and dichotomous operationalizations, respectively. Descriptive statistics will be provided for all variables, and inferential models related to Specific Aim 2 will assume three complementary but parallel analytical approaches. First (H2_a), an observed treatment effects dosage response analysis will test for observed associations between attendance to the weekly sessions and reductions in both the magnitude (negative binomial) and/or likelihood (logistic) of engagement in HIV sexual risk behaviors [note: sexual risk behavior data is gathered during standard *Getting Off* procedures]; analyses will be double-robustly estimated to ensure proper model specification.¹¹ Second (H2_b), the same model will be estimated, but will further include participants' CESD-R depression scores both as a main effect, as well as in a statistical interaction term with the number of sessions attended. Planning such a nested analysis allows for full specification of the effects of depression, both directly and in response to the intervention. Third (H2_c), participants' HIV sexual risk behavior outcomes will be statistically contrasted against those same outcomes from a group of historical matched controls sampled from the program (2009-2017) and matched using either caliper or nearest neighbor algorithm (based on method of best fit)¹² using participant age, race/ethnicity, HIV status, and the severity of their use. The proposed Secondary Aim will be tested using the Bernoulli family and logistic link function, where uptake or satisfactory (i.e., $\geq 85\%$) adherence to ART/PrEP during the course of the intervention will be coded a "1", "0" otherwise, and regressed on intervention exposure and/or CESD-R depression scores.

Missing Data

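### The historical-control comparison (H2_c) is stated as a difference in reductions, but nothing in its matching or model requires baseline sexual risk, so a follow-up-only contrast is permitted

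*Combined protocol and SAP*

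**What the plan says.** Under Specific Aim 2, H2_c states that, relative to historical matched controls, "participants receiving sessions will demonstrate greater reductions in HIV sexual risk behavior". Study Design adds that "Getting Off program evaluation data from study participants will be matched and compared with historical program evaluation data", and gives the purpose as "to assess the impact of the MoodGym intervention on the Getting Off program outcomes through an observed treatment effects analysis".

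Statistical Analyses puts H2_c into practice in one sentence: "HIV sexual risk behavior outcomes will be statistically contrasted against those same outcomes from a group of historical matched controls sampled from the program", with controls from 2009-2017 matched "using participant age, race/ethnicity, HIV status, and the severity of their use". For H2_c that sentence names no time point, change score, baseline covariate or group-by-time term.

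Three other statements in the same section bear on the point:
- A general covariate rule: "sociodemographics or other variables found to significantly influence primary outcomes may be tested for inclusion as statistical controls".
- A clause in the H2_a sentence: "analyses will be double-robustly estimated to ensure proper model specification". It lists no covariates.
- A bracketed remark on the data source, "note: sexual risk behavior data is gathered during standard", which ends by naming the program's procedures.

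**The concern.** A claim about reductions needs a starting value in both groups. The four matching variables leave out the one most closely tied to the outcome, its own pre-treatment level, and no model term is required to bring it in. The study is single-arm and its controls come from earlier years, so nothing in the design makes the groups equal at baseline.

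H2_c is the study's only comparison with people outside the study. Suppose only follow-up values are contrasted. If participants start at higher risk than their matched controls, the comparison leans against an inert MoodGym; if they start lower, it leans in its favor. How the baseline is used can decide the sign of the estimate, and the plan leaves that choice open until the data are in hand.

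**Working it through.** **The plan's own figure.** Table 1 gives 6 enrolled per month over 7 marked months: 6 x 7 = 42, as stated. The plan gives no alpha, power, SD, baseline gap, correlation or number of controls, so it has no error rate to reproduce.

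**Inputs.** From the documents: 42 participants. Assumed: 42 controls (1:1 matching), no MoodGym effect, two-sided 5% test, unit SD at both times, baseline/follow-up correlation r = 0.3, 0.5 or 0.7, and a gap after matching of d = 0.3 SD or 0.1 SD. A positive gap means participants start at higher risk.

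**Formulas.** Let the gap at follow-up be k x d. With k = r the gap regresses toward a common mean; with k = 1 it is stable.
- Follow-up only: bias kd; SE = sqrt(2/42) = 0.218.
- Change: bias (k - 1)d; SE = sqrt(2/42 x 2(1 - r)) = 0.258, 0.218, 0.169.
- Baseline-adjusted: bias (k - r)d; SE = sqrt(2/42 x (1 - r^2)) = 0.208, 0.189, 0.156.
- Rejection probability, with z = bias/SE: 1 - Phi(1.96 - z) + Phi(-1.96 - z).

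**Example.** Follow-up only, d = 0.3, r = k = 0.5: bias 0.5 x 0.3 = 0.15; z = 0.15/0.218 = 0.69; rejection 10.6%.

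**Results for d = 0.3**, as bias in SD (rejection rate), for r = 0.3, 0.5, 0.7:

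| Analysis | Gap regresses (k = r) | Gap stable (k = 1) |
|---|---|---|
| Follow-up only | 0.09 (7.0%), 0.15 (10.6%), 0.21 (16.1%) | 0.30 (28.0%) at each r |
| Change | -0.21 (12.9%), -0.15 (10.6%), -0.09 (8.3%) | 0 (5%) |
| Baseline-adjusted | 0 (5%) | 0.21 (17.2%), 0.15 (12.5%), 0.09 (8.9%) |

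**Smaller gap.** For d = 0.1 the follow-up-only bias is 0.03 to 0.10 SD and the rejection rate 5.2% to 7.4%.

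**When adjustment helps.** Its bias is smaller in size than the follow-up-only bias when |k - r| < |k|, that is, when k > r/2. For r <= k <= 1 the adjusted and change estimates lie on either side of the truth. If the gap vanishes by follow-up (k = 0) with r = 0.5 and d = 0.3, follow-up only has bias 0 (5%) and the adjusted model -0.15 (12.5%).

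**Check on the count scale.** A simulation (1,500 runs per cell, log-normal subject rates, participants' baseline rate 1.35 times the controls', robust SEs) gave these rate ratios with no MoodGym effect, for r = 0.3 to 0.7. Values above 1 count against MoodGym.
- Gap regresses: follow-up only 1.09 to 1.22; adjusted 1.01 to 1.02; group-by-time 0.80 to 0.90.
- Gap stable: follow-up only 1.35 to 1.34; adjusted 1.26 to 1.13; group-by-time 0.99 to 1.00.

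The pattern is the same. With no gap, rejection rates in that simulation were already 5.2% to 8.0%, so its lowest follow-up-only rate (7.9%, r = 0.3, gap regresses) shows no clear excess, although the ratio is shifted to 1.09.

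**The case against.** **The change-based reading is natural.** H2_c speaks of reductions. The Statistical Analyses section describes the three Aim 2 approaches as parallel, and the first of them models reductions. The outcomes contrasted in H2_c may well be meant as reductions. This stands: a reader might infer that the plan commits to a follow-up-only comparison, and the documents do not support that. What remains is that reduction is not defined for H2_c and that the text allows either analysis.

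**Other clauses may bring the baseline in.** Study Design uses for the historical comparison the same observed-treatment-effects label that H2_a carries, so double-robust estimation may be meant to extend to H2_c. The covariate rule could also admit baseline risk. But the first clause lists no covariates, and the second is discretionary and rests on a significance screen. Neither requires baseline sexual risk.

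**The gap is assumed.** Both groups come from the same program, and matching on HIV status and severity of use may shrink a difference in sexual risk. This stands. At 0.1 SD the effect on the error rate is slight.

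**Adjustment is not always better.** A reader might infer that a baseline covariate always improves on a follow-up-only contrast, or that the adjusted model should be primary. Neither follows. Adjustment is the more biased of the two when the gap shrinks below half of r times its baseline size, and it is itself biased when the gap is stable. The documents do not say which pattern holds.

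**This is a pilot.** It aims to estimate and states no confirmatory rule. That limits the severity, but a shifted estimate is a problem for estimation as well as for testing.

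**Conclusion.** The concern holds in a limited form. It is certain from the text that no matching variable and no required model term for H2_c brings in baseline sexual risk, and that a follow-up-only contrast is therefore permitted alongside a change-based one. The size and direction of any resulting bias cannot be known from the documents. The calculated error rates show sensitivity under an assumed gap, correlation and number of controls; they do not forecast this study's bias. Under those assumptions the harm ranges from negligible at 0.1 SD to substantial for a stable gap of 0.3 SD. Neither the change model nor the adjusted model is best under every pattern, so the choice has to be made and justified in advance. This should be fixed before the H2_c data are analyzed.

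**What to change.** In the H2_c paragraph of Statistical Analyses:

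1. Define reduction, and require baseline sexual risk in the analysis by pre-specifying two models. The first is a group-by-time (change) model, which fits the wording of the hypothesis and assumes that both groups would have changed in parallel without MoodGym. The second is the follow-up model (negative binomial or logistic) with baseline sexual risk as a covariate, for example log(1 + baseline count). It assumes that any remaining gap regresses toward a common mean.
2. State which model is primary and why. Report both estimates, and describe the result as dependent on the assumption if they disagree.
3. Report the balance of baseline sexual risk after matching.
4. Use the same assessment times in participants and controls.

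The cost is SAP wording, one further model and a balance table. Sexual risk data are already collected by the program, but it must be confirmed that the 2009-2017 files hold baseline values measured comparably. Neither model removes calendar-time or self-selection differences between participants and historical controls, and the report should say so.

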MoodGym Implementation					X	X	X	X	X	X	X	X	X
Data Cleaning & Analysis													X
Begin Publication & Dissemination													X

STATISTICAL CONSIDERATIONS

Assessments

1. Center for Epidemiologic Studies Depression Scale (Revised). The Center for Epidemiologic Studies Depression Scale (Revised) [CESD-R]⁹ is a widely used depression assessment which consistently shows strong psychometric properties and concurrent validity with clinical diagnostic instruments.¹⁰ The CESD-R will be administered at the start of each session.

2. ART and PrEP Uptake and Adherence. Administered at baseline enrollment in the pilot study and 3-month follow-up only. The ART and PrEP Uptake and Adherence form briefly queries HIV-positive and HIV-negative participants as to whether they have begun and/or adhered to a prescribed ART or PrEP regimen in the past 3 months.

Statistical Analyses

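### The Secondary Aim outcome pools starting ART/PrEP with taking at least 85% of it, so a positive result cannot show which of the two changed

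*Combined protocol and SAP*

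**What the plan says.** The Secondary Aim is to be analysed by logistic regression (Statistical Considerations, Statistical Analyses). The outcome is 1 "where uptake or satisfactory" (at least 85%) "adherence to ART/PrEP during the course of the intervention will be coded a '1', '0' otherwise". It is then "regressed on intervention exposure and/or CESD-R depression scores".

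The hypothesis, H3_a in the specific aims, names both behaviours together. Its last clause, picking up at the end of the phrase on HIV-positive men, reads "positive participants as well as increased likelihood of PrEP uptake and/or adherence for HIV-negative participants". The Background gives a reason that concerns adherence only: "depression is an obstacle to medication adherence for both HIV-positive and HIV-negative MSM".

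The data come from the ART and PrEP Uptake and Adherence form (Assessments), which is "Administered at baseline enrollment in the pilot study and 3-month follow-up only". It asks men "whether they have begun and/or adhered to a prescribed ART or PrEP regimen in the past 3 months".

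The Missing Data section sorts follow-up assessments into three states: observed, intermittently absent, or lost through dropout. It mentions imputation as one possible strategy if the missingness proves non-ignorable. It does not say how a man without a 3-month form is scored on the Secondary Aim outcome.

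**The concern.** The word joining the two parts of the rule is an or. A man who begins PrEP and takes 20% of his doses scores 1; a man continuing ART at 84% scores 0. The second case alone would be unremarkable, since any cut-point has a near miss. What matters is that the cut-point is applied to one group of men and not to the other.

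The stated reason for expecting an effect is that depression lowers adherence. In new starters the coded outcome carries no information on adherence. If the odds of a 1 rise with attendance, or fall with CESD-R score, the trial cannot say whether the intervention is linked to starting medication, to taking it, or to both. These are different findings, and a pilot is meant to tell the next study which of them to pursue.

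A lesser point is that the residual 0 carries no exception for men whose follow-up status is unknown, so two analysts could score the same man differently.

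**Working it through.** **Inputs from the documents.** Planned enrolment is 42 (Table 1). This reproduces: 6 per month × 7 enrolment months = 42. The adherence threshold is 85%. The documents give no expected rate of starting, adherence or form return, so every rate below is an assumption shown over a range.

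**1. What the rule does to each man with a completed form**

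| Status at follow-up | Share of doses taken | Code |
|---|---|---|
| Started during the study | 85% or more | 1 |
| Started during the study | under 85% | 1 |
| Already on a regimen | 85% or more | 1 |
| Already on a regimen | under 85% | 0 |
| Not on a regimen | none | 0 |

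The first two rows get the same code, so the outcome cannot separate them.

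**2. How many men this could involve.** Let s be the share of the 42 who start and q the share of starters who take less than 85%. Men scored 1 while under 85% = 42 × s × q. Starters at 85% or more, as a share of all 42 = s × (1 − q). Men already on a regimen at baseline are left out of this count.

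| s | q | Scored 1 by starting | Starters at 85% or more | Scored 1 but under 85% |
|---|---|---|---|---|
| 30% | 10% | 30% | 27% | 1.3 men |
| 30% | 30% | 30% | 21% | 3.8 men |
| 30% | 50% | 30% | 15% | 6.3 men |
| 50% | 10% | 50% | 45% | 2.1 men |
| 50% | 30% | 50% | 35% | 6.3 men |
| 50% | 50% | 50% | 25% | 10.5 men |
| 70% | 10% | 70% | 63% | 2.9 men |
| 70% | 30% | 70% | 49% | 8.8 men |
| 70% | 50% | 70% | 35% | 14.7 men |

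With fewer starters, say 6 to 12 men of whom 30% to 50% take less than 85%, the count runs from 6 × 0.3 = 1.8 to 12 × 0.5 = 6.0 men, or 4% to 14% of 42.

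Within each value of s the third column does not move while the fourth does. Adherence among starters could almost halve (45% to 25% of the cohort at s = 50%) without changing the coded outcome.

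**3. Missing forms, if they were scored 0.** This step applies only if the residual 0 is read literally. Coded rate = true rate × share of forms returned. Take a true rate of 50% at every attendance level, with 10% of forms missing among high attenders and 40% among low attenders:

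- coded rates: 0.50 × 0.90 = 45% and 0.50 × 0.60 = 30%
- odds ratio: (0.45/0.55) ÷ (0.30/0.70) = 1.91

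With true rates of 30% to 70% and 20% to 40% missing among low attenders, the odds ratio runs from 1.17 to 2.35. With 20% missing in both groups it is 1.0. The distortion therefore needs loss that depends on attendance as well as the literal reading.

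**The case against.** The strongest reply is that the pooling is deliberate. The Secondary Aim, H3_a and the form all name uptake and adherence together, and the coding follows them. A reader might infer from the 20% and 84% examples that the rule misclassifies men. The documents do not support that: under the outcome as defined, a starter is correctly a 1. It is also not shown that adherence goes unrecorded in starters. Nothing in Assessments excludes them from the adherence question, and the plan promises descriptive statistics for all variables. All of this stands. What remains is that the only inferential outcome specified for this aim cannot be read as adherence.

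A reader might also infer that the residual 0 turns loss to follow-up into failure and so builds an attendance-success association into the data. That needs two things that the documents do not state: that a missing form is scored 0, and that low attenders lose more forms. The Missing Data section points away from the first, because it treats absent follow-up data as a category of its own and contemplates imputation, and scoring absent forms 0 would leave nothing to impute for this outcome. In the plan's defence, a 1, and 0 otherwise, is also common shorthand for a binary indicator. What stands is narrower: the two sections are never tied together, and a missing-data strategy is named only conditionally.

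Finally, this is a secondary aim of a single-arm pilot with no power claim. The consequence is for interpretation and does not touch the sexual risk outcome.

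**Conclusion.** The point holds as one of interpretation. The Secondary Aim outcome combines two behaviours, the 85% standard never reaches new starters, and a positive result could not be attributed to starting or to adherence. That follows from the wording alone and needs no assumed rate.

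Its size does depend on assumptions. Over 30% to 70% of the 42 men starting, and 10% to 50% of starters taking less than 85%, between 1.3 and 14.7 men would be scored 1 while below the adherence standard (6.3 men at 50% and 30%). The documents give nothing with which to narrow that range.

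The handling of missing forms is an ambiguity to clear up and not a demonstrated bias. The odds ratios in step 3 show what the literal reading would do under attendance-related loss; they do not predict what this trial will find. Overall, this is a low-cost improvement to a secondary analysis.

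**What to change.** Keep the pooled H3_a outcome if it is wanted, and add two component outcomes from the same form:

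1. **Uptake:** started ART or PrEP by follow-up, among men not on it at baseline.
2. **Adherence:** at least 85% at follow-up, among men on a prescribed regimen, with starters held to the same 85%.

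State the denominator for each.

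As a clarification, say that a 0 requires a completed 3-month form, that a man without one is missing and is handled under the Missing Data section, and that scoring missing as 0 is a labelled sensitivity analysis.

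The cost is SAP wording and, provided the form records adherence for starters as well as continuing users, no new data collection; that should be confirmed before the text is finalised. The real price is smaller denominators. Each component uses only part of a cohort of 42, a logistic model may not be estimable, and the component results may have to be descriptive. The adherence component is also conditional on being on a regimen at follow-up, which the intervention might itself affect, so it should be reported beside uptake and not alone.

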General Estimation Equation (GEE) analyses will test patterns of missing data in the follow-up assessments. Follow-up assessment data will be coded trichotomously (i.e., observed, intermittent missing, missing due to dropout) and regressed on arm assignment and relevant covariates (e.g., racial/ethnic identity, age) to ensure appropriate application of inferential logic. If a non-ignorable pattern of missing data is discovered (note: confirmed by Little's test of non-random missingness), sensitivity analyses will be conducted to ascertain which missing data management strategy (e.g., multiple partial imputation) should be applied.

DATA COLLECTION AND CONFIDENTIALITY

MoodGym Online Modules

The online modules do not report any sensitive data related to participants' mental health. All usage measures will be based on the recording of the modules completed by each participant during weekly sessions, and depression symptoms and trends are assessed via the weekly CESD-R assessments.

Study Counselor-Administered Assessments

The will briefly assess participants' depression symptoms (via the CESD-R) at the

beginning of each weekly session, and HIV-related medication uptake/adherence (via the ART and PrEP Uptake and Adherence form) at baseline and 3 month follow-up. In both cases, assessments will be administered via an online data entry form administered from the same computer the sessions are accessed. The online data entry form and short-term data hosting will be contracted using Qualtrics, a global data entry firm Friends Research Institute has ongoing multi-year contracts providing access to online survey creation and implementation software. The Qualtrics' system is HIPAA compliant and conforms to industry standard (e.g., ISO 27001 and FEDRAMP compliant) encryption and data security. Study data will be hosted on the Qualtrics cloud for the duration of the study, and will be removed at the completion of the data collection phase.

MONITORING AND ADVERSE EVENT REPORTING

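### The Secondary Aim logistic model plans no baseline ART/PrEP term, although the form is completed at baseline, so its attendance (or CESD-R) association can be confounded in either direction

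*Combined protocol and SAP*

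**What the plan says.** Under Statistical Analyses, the Secondary Aim endpoint is binary: uptake, or satisfactory (at least 85%) "adherence to ART/PrEP during the course of the intervention will be coded a" 1, and 0 otherwise. The model is logistic, with the endpoint "and regressed on intervention exposure and/or CESD-R depression scores". No other predictor is named, the analysis set is not restricted by baseline status, and no change outcome is defined.

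Baseline information is nevertheless collected. Assessments, item 2, says of the ART and PrEP Uptake and Adherence form: "Administered at baseline enrollment in the pilot study and 3-month follow-up only". The form asks "whether they have begun and/or adhered to a prescribed ART or PrEP regimen in the past 3 months". The section on Study Counselor-Administered Assessments repeats the schedule: "HIV-related medication uptake/adherence (via the ART and PrEP Uptake and Adherence form) at baseline and 3 month follow-up".

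The only general covariate provision, at the start of Statistical Analyses, is that "sociodemographics or other variables found to significantly influence primary outcomes may be tested for inclusion as statistical controls". On design, the Study Design section states: "This study is a single-arm, non-randomized pilot study".

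**The concern.** Whether a man was already taking ART or PrEP reliably when he enrolled is likely to be a strong predictor of whether he is at follow-up. There is no randomised comparison, so the exposure is how many sessions each man chose to attend. If men who were already adherent attend more, attendance will be associated with adherence for reasons that predate MoodGym. If they attend less, a real benefit could be masked. The same applies to CESD-R if baseline ART/PrEP status is related to depression scores.

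At stake is the reading of the Secondary Aim, which is framed as estimating an effect of MoodGym on uptake and adherence. The variable that would remove most of this ambiguity is already on the baseline form but has no role in the model.

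**Working it through.** **Inputs from the documents.** Table 1 (Timeline) gives enrolment of 6 per month over seven marked months: 6 × 7 = 42, which matches the stated target. Up to seven sessions are available (Incentive Schedule). No significance level, power, effect size or ART/PrEP rate is stated for this aim, so there is no other planned figure to reproduce.

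**Assumed inputs.** Baseline adherence p0 = 0.4, 0.5 or 0.6; 90% of baseline adherents coded 1 at follow-up; 15% of the others coded 1; MoodGym inert; ART and PrEP pooled, n = 42. Attendance differs between baseline-adherent and other men by d standard deviations (SD).

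**Step 1: how many of the 1s are carry-over.** Share = p0 × persist / [p0 × persist + (1 − p0) × convert].
- At p0 = 0.5: 0.45 / (0.45 + 0.075) = 0.86. At p0 = 0.4: 0.36 / 0.45 = 0.80. At p0 = 0.6: 0.54 / 0.60 = 0.90.
- Over a wider assumed range (30-70% baseline adherence, 80-90% persistence, 10-30% conversion), the lowest value is 0.24 / (0.24 + 0.21) = 0.53 and the highest is 0.63 / (0.63 + 0.03) = 0.95.

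**Step 2: size of the confounding, by approximation at p0 = 0.5.** The overall rate is 0.525, with variance 0.525 × 0.475 = 0.249. The risk difference by baseline status is 0.90 − 0.15 = 0.75.
- With d = 0.5 and a within-group SD of 1, cov(attendance, baseline) = 0.5 × 0.25 = 0.125 and var(attendance) = 1 + 0.25 × 0.25 = 1.0625.
- The unadjusted log odds ratio is about (0.75 × 0.125 / 1.0625) / 0.249 = 0.35, so the odds ratio is about 1.4. With d = −0.5 it is the reciprocal, about 0.7.
- The standard error is about 1 / √(42 × 0.249 × 1.0625) = 0.30, so the expected z is about 1.18. A two-sided 5% test would then reject in roughly 22%.

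**Step 3: simulation at n = 42, no true effect, nominal 5%.**

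| Attendance difference (adherent minus other) | Without baseline term | With baseline term (Firth) |
|---|---|---|
| 0 | 4-5% | 3-5% |
| 0.25 SD | 8-9% | 3-5% |
| 0.5 SD | 17-21%, OR about 1.4 per SD | 3-5%, OR about 1.0 |

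A run with different assumptions (85% persistence, 20% conversion, 30-70% adherent at baseline, mean attendance 4.9 versus 4.2 of 7 sessions) gave 17-22% without the term and about 6% with it.

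**Step 4: the other direction.** With d = −0.5 the null odds ratio is about 0.7. A true conditional log odds ratio of 0.8 per SD then appears as an odds ratio of about 1.1, with 5-6% rejection.

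**Step 5: fitting and a coarse baseline item.** The unpenalised adjusted fit failed or separated in 14-22% of runs, while the Firth fit converged in all. If the form yields only a coarse yes/no baseline item, rejection at 0.5 SD is 6-7% (10% misclassified each way) or 8-10% (30% of non-adherent men answering yes). Adjustment then helps but does not fully remove the bias.

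**Step 6: precision and power.** Within baseline groups the mean outcome variance is 0.5 × (0.9 × 0.1) + 0.5 × (0.15 × 0.85) = 0.109, against 0.249 overall. The ratio of standard errors is about √(0.249 / 0.109) = 1.5, in line with the simulated 0.33 and 0.49. With no link between baseline status and attendance and a true log odds ratio of 0.8 per SD, rejection was about 22% unadjusted and 32-39% adjusted.

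**Limits.** Only the attendance version of the model was calculated; the CESD-R version rests on the same argument without a figure. Separate fits for HIV-positive and HIV-negative men would have fewer than 42 each.

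**The case against.** **The covariate clause already allows this.** It does allow it, but it does not plan it. The clause is permissive, depends on significance, and is tied to primary outcomes, whereas the outcome of primary analytical interest is sexual risk behavior. Double-robust estimation is specified for the H2_a dose-response analysis, not for the Secondary Aim.

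**Counting a man who merely stays adherent as a success is what the aim intends.** This stands. A reader might infer from the carry-over share that the coding is wrong. H3_a predicts that more attendance "will be associated with lower comorbid depression scores which, in turn, will be associated with increased likelihood of ART medication uptake" and/or adherence, so maintained adherence is a legitimate success for a man already on treatment. The coding matters here only because, without a baseline term, it lets prior status enter the attendance association.

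**Nothing shows that adherent men attend more.** This also stands. A reader might infer that the plan will produce a spurious benefit. The documents give no relation between baseline status and attendance. If there is none, the test is not inflated; if it is negative, the bias runs against MoodGym.

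**42 men are too few to adjust.** The wider interval is real, but it is not lost power. The adjusted odds ratio is a conditional quantity that lies further from 1 when there is an effect, and the chance of detecting an effect did not fall in simulation.

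**It is a secondary aim in a feasibility pilot.** This limits the weight of the point. The plan still calls for an inferential test, and the remedy needs no new data.

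**Conclusion.** The point holds as a specification gap: a strong likely confounder of a self-selected exposure is collected at baseline and left out of the planned model. Under the stated assumptions the false-positive rate ranges from nominal (no attendance difference) to about 17-21% (0.5 SD), with a null odds ratio of about 1.4 or 0.7 per SD depending on direction. Between 53% and 95% of outcomes coded 1 could be continuation rather than change. Only n = 42 comes from the documents, so these figures illustrate what could happen and do not predict it.

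Three neighbouring matters are queries for the sponsor and not part of this finding: the endpoint period against the form's three-month recall, whether the form records percent adherence, and how the mediation chain in H3_a would be estimated. A reader might take them as further errors in this model. The first two turn on detail the documents do not show, and the third is a separate question. The sexual-risk analyses under Specific Aim 2 are not affected.

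**What to change.** Prespecify baseline ART/PrEP status, as recorded on the existing form, as a covariate in the Secondary Aim logistic model. Fit it with a method that tolerates separation, Firth's penalised likelihood being one option. Report a table of follow-up status by baseline status, so that new uptake and maintained adherence can be seen apart. If the form gives only a coarse yes/no baseline item, adjust for that item and state that some confounding may remain.

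The cost is a change of plan wording and one table, with no new visit or questionnaire. Intervals for the log odds ratio will be about 1.5 times wider. The plan should say that the adjusted odds ratio is conditional on baseline status, so that the wider interval is not mistaken for a loss of power.
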